9.5.1.3.3 CEREBROSPINAL FLUID SAMPLING

Amyloid CSF is 1 of the 2 methods required at screening to determine subject eligibility for the study. Subjects that undergo the eligibility CSF sample collection or who consent to the CSF longitudinal substudy will be encouraged to stay at the site after completion of LP for medical observation. CSF sample(s) will be collected by LP (gravity drip method only) after fasting (preferred), or at least 2 hours after the most recent meal. Further guidance for the timing of CSF collection is provided in [Section 9.5.1.4.2](#)

Subjects who provide a CSF sample at Screening for amyloid eligibility purposes, but did not initially consent to the CSF longitudinal substudy may provide consent to the CSF longitudinal substudy at any point in time up to Visit 13 (or ED). INR testing should be performed for subjects who consent to provide a CSF sample and who have a medical condition with bleeding risk that is not under adequate control. (revised per Amendment 01)

9.5.1.4 Pharmacokinetic, Pharmacodynamic, Pharmacogenomic, and Other Biomarker Assessments

9.5.1.4.1 PHARMACOKINETIC ASSESSMENTS

Blood samples will be collected for the determination of the concentrations of E2609 in all randomized subjects. Analyses of metabolite concentrations may be performed, depending on emerging data from other studies with E2609.

Samples from all subjects receiving active treatment will be analyzed. In addition, a predetermined percentage of placebo samples will be analyzed. Remaining placebo samples will be held in storage in the event that further confirmatory analysis is requested. Plasma concentrations of analytes will be quantified by liquid chromatography with tandem mass spectrometry methodology using a previously validated assay.

Blood samples will be collected as specified in [Table 2](#) and [Table 3](#). Two plasma PK samples will be obtained at each of the following visits: 1 sample at predose (trough) and another sample 1 to 6 hours postdose at Visits 3, 4, 6, 7, 9, and 11 and another sample 4 to 8 hours postdose at Visit 13 (or ED). Therefore, subjects or their study partners must be instructed not to take their study drug at home on the day the PK sampling is performed. Instead, subjects will take the study drug at the clinic after collection of the predose PK sample. At Visit 13 (or ED) the PK blood sample should be collected shortly before or after

completing the LP for subjects participating in the CSF substudy. If at an ED Visit, the subject has already stopped study drug, then no dosing will take place, but the trough PK sample will still be collected. For subjects participating in the CSF substudy who have stopped taking study drug prior to the ED visit, the LP should be performed at approximately the same time as at the Screening Visit, and then a trough PK sample will be collected either shortly before or shortly after the LP.

Blood will also be drawn where possible at the first report of an SAE or severe unexpected AE and at its resolution.

See the laboratory manual (to be supplied to study sites) for a description of the collection, handling, and shipping procedures for PK samples.

9.5.1.4.2 PHARMACODYNAMIC, PHARMACOGENOMIC, AND OTHER BIOMARKER, ASSESSMENTS

Biomarkers

The CSF sample will be used for PD assessments including but not limited to CSF A β (1-x), A β (1-42), A β (1-40), t-tau, p-tau, and BACE1 levels and activity.

The plasma sample will be used for A β (1-x) analysis and may be used for exploratory biomarker analyses. A β (1-x) in both CSF and plasma will be measured using a modified commercially available enzyme-linked immunosorbent assay (ELISA). The prescreening and postscreening analysis of CSF A β (1-42), A β (1-40), t-tau, and p-tau will be performed using commercially available ELISAs. BACE1 levels will be measured using internally developed fluorescence resonance energy transfer and ELISA based assay(s). Substrates of BACE1 inhibition may also be explored using Western blots or other amenable methodology if clinical observations warrant and if analytes can be reliably tested in samples collected.

Blood samples will be collected for PD assessments as specified in [Table 2](#) and [Table 3](#). The blood sample collected for PD analyses at Screening should be collected at fasting or at least 2 hours after the most recent meal and PD blood samples should be taken predose at Visits 3, 4, 6, 7, 9, 11, and 13 (or ED) and, as far as is feasible, samples should be taken at the same time of day

Blood samples and CSF (if applicable) collected at Screening will be stored for determination of prior exposure to any suspected infective agents in the event that the subject develops TEAEs that warrant further investigation (eg, treatment-emergent infection). Testing may include, but not be limited to, serological tests (eg, HSV1 and 2), viral titer by quantitative polymerase chain reaction (Q-PCR), and/or human leukocyte antigen (HLA) genotyping.

For all subjects, baseline and on-study blood samples, DNA samples, and any collected CSF samples (if applicable) will be stored for up to 15 years.

See the laboratory manual (to be supplied to study sites) for a description of the collection, handling, and shipping procedures of the biomarker samples.

Pharmacogenomics

A blood sample will be obtained at Screening and will be used to determine the *ApoE* genotype of subjects enrolled in this study. The findings will be used in the statistical analysis to determine the effects on treatment response and safety. (revised per Amendment 01)

The genomic DNA samples will be stored and may also be used to examine the role of genetic variability in subjects' absorption, distribution, metabolism, and excretion, the development of AEs, or underlying AD. Variations in E2609 exposure or the occurrence of AEs observed in the study population may be evaluated by correlation of single-nucleotide polymorphisms with PK, safety, or PD data.

Details of PGx testing may be provided and reported separately.

Amyloid PET

An amyloid PET scan may be performed at Screening to confirm deposition of amyloid in the brain. A historical amyloid positive PET scan may be used if conducted within 12 months before the planned date of randomization and provided that the scan and result are considered acceptable by the central PET reading group. As part of an optional substudy, longitudinal amyloid PET imaging will also be conducted after 12 and 24 months of treatment (or at ED, provided the subject has received at least 39 weeks of study drug). Longitudinal amyloid PET imaging will only be conducted on subjects that have consented to this optional substudy and who have had Screening PET scans performed for this study (ie, historical scans cannot be used for the longitudinal analyses).

Descriptions and detailed instructions for all amyloid PET imaging can be found in the PET imaging manual provided to the study PET imaging facilities.

Further details regarding pharmacodynamics, pharmacogenomics, and other biomarker research is provided in [Appendix 4](#).

9.5.1.5 Safety Assessments

Safety assessments will consist of monitoring and recording all AEs and SAEs; regular monitoring of hematology, blood chemistry, and urinalysis; periodic measurement of vital signs and ECGs recordings evaluated by a central reader; physical, dermatologic and neurologic examinations; assessment of suicidality (using the C-SSRS or the clinical assessment of suicidality as outlined in [Table 2](#) and [Table 3](#)); and MRIs as detailed in [Table 2](#) and [Table 3](#). Subjects reporting AEs relating to abnormal dreams, nightmares, or sleep terror will be questioned on the nature, frequency, and impact of these events. (revised per Amendment 01) Blood samples for immunologic assessments will be collected as outlined in [Table 2](#) and [Table 3](#). Some of the immunologic assessment blood sample will be used to prepare isolated PBMCs which will be stored for testing. The results of some of the immunologic assessments will be provided to the DSMB for periodic review during the study. (revised per Amendment 01)

9.5.1.5.1 ADVERSE EVENTS AND EVENTS ASSOCIATED WITH SPECIAL SITUATIONS

An AE is any untoward medical occurrence in a subject or clinical investigation subject administered an investigational product. An AE does not necessarily have a causal relationship with the medicinal product. For this study, the study drug is E2609.

The criteria for identifying AEs in this study are:

- Any unfavorable and unintended sign (including an abnormal laboratory finding), symptom, or disease temporally associated with the use of an investigational product, whether or not considered related to the investigational product (Note: Every sign or symptom should not be listed as a separate AE if the applicable disease [diagnosis] is being reported as an AE)
- Any new disease or exacerbation of an existing disease
- Any deterioration in nonprotocol-required measurements of a laboratory value or other clinical test (eg, ECG or x-ray) that results in symptoms, a change in treatment, or discontinuation of study drug
- Recurrence of an intermittent medical condition (eg, headache) not present pretreatment (Baseline)
- An abnormal laboratory test result should be considered an AE if the identified laboratory abnormality leads to any type of intervention, withdrawal of study drug, or withholding of study drug, whether prescribed in the protocol or not.

All AEs observed during the study will be reported on the eCRF. All AEs, regardless of relationship to study drug or procedure, should be collected beginning from the time the subject signs the study ICF through the last visit (Visit 15, as shown in [Table 3](#)). Subjects who fail screening primarily due to AE(s) must have the AE(s) leading to screen failure reported on the Screening Disposition eCRF and the Adverse Event eCRF. SAEs will be collected for 12 weeks after the last dose.

Abnormal laboratory values should not be listed as separate AEs if they are considered to be part of the clinical syndrome that is being reported as an AE. It is the responsibility of the investigator to review all laboratory findings in all subjects and determine if they constitute an AE. Medical and scientific judgment should be exercised in deciding whether an isolated laboratory abnormality should be classified as an AE. Any laboratory abnormality considered to constitute an AE should be reported on the Adverse Event eCRF.

Abnormal ECG (QTc) results, if not otherwise considered part of a clinical symptom that is being reported as an AE, should be considered an AE if the QTc interval is more than 450 ms and there is an increase of more than 60 ms from baseline. If the QTcF is greater than 450 ms on the first single 12-lead ECG, 2 additional 12-lead ECGs will be performed 1 minute apart and the mean of the 3 QTcF values will be calculated. Any ECG abnormality that the investigator considers as an AE should be reported as such.

Cognitive decline will be assessed as a safety assessment in addition to an efficacy assessment. Cognitive assessments include the CDR, ADAS-cog₁₄, and MMSE (see [Section 9.5.1.3.1](#)). If these assessments show cognitive decline during the Treatment Period, and if this cognitive decline is considered by the investigator to be excessive relative to the subject's recent AD history, this finding should be reported as an AE. It is the responsibility of the investigator to review the cognitive assessments and to determine if any result constitutes an AE.

AEs that might indicate signals of possible drug abuse potential will require a more detailed follow-up through completion of a specific eCRF form. This includes AEs that fall into the following categories and examples of such AEs are provided in [Appendix 3](#).

- Euphoric mood
- Elevated mood
- Feeling abnormal
- Feeling drunk
- Feeling of relaxation
- Thinking abnormal
- Hallucination
- Inappropriate affect
- Mood disorders and disturbances
- Drug tolerance
- Psychosis
- Dissociative state

It is also the responsibility of the investigator to review the results of the C-SSRS/clinical assessment of suicidality in all subjects and determine if any result constitutes an AE. Medical and scientific judgment should be exercised in deciding whether an isolated suicidality rating scale response should be classified as an AE (see [Section 9.5.1.5.9](#) for a description of the C-SSRS and of the clinical assessment of suicidality).

The following adverse events will require the collection of information sufficient to provide a detailed description of the event, treatment, and outcome to the Medical Monitor for the study: any treatment-emergent significant laboratory abnormality; any seizures, herpes zoster infection, severe infection; any moderate to severe drug rash or any rash lasting more than 72 hours (regardless of severity); amyloid-related imaging abnormalities (cerebral vasogenic

edema, macrohemorrhage, an area of superficial siderosis, or a new microhemorrhage); a positive suicidality assessment on either the C-SSRS or the clinical assessment of suicidality

All AEs must be followed for 12 weeks after the subject's last dose, or until resolution, whichever comes first. Subjects who have a Grade 2 or greater lymphocytopenia (less than 800/mm³) during the follow-up period (ie, at either Visit 14 or Visit 15) should have absolute lymphocyte count measured every 4 weeks until resolution or confirmation of a non drug-related cause of the lymphocytopenia. (revised per Amendment 01) All SAEs must be followed to resolution or, if resolution is unlikely, to stabilization.

Every effort must be made by the investigator to categorize each AE according to its severity and its relationship to the study treatment.

Assessing Severity of AEs

AEs will be graded on a 3-point scale (mild, moderate, severe) and reported in the detail indicated on the eCRF. The definitions are as follows:

Mild	Discomfort noticed, but no disruption of normal daily activity
Moderate	Discomfort sufficient to reduce or affect normal daily activity
Severe	Incapacitating, with inability to work or to perform normal daily activity

The criteria for assessing severity are different than those used for seriousness (see [Section 9.5.1.5.2](#) for the definition of an SAE).

Assessing Relationship to Study Treatment

Items to be considered when assessing the relationship of an AE to the study treatment are:

- Temporal relationship of the onset of the event to the initiation of the study treatment
- The course of the event, especially the effect of discontinuation of study treatment or reintroduction of study treatment, as applicable
- Whether the event is known to be associated with the study treatment or with other similar treatments
- The presence of risk factors in the study subject known to increase the occurrence of the event
- The presence of nonstudy, treatment-related factors that are known to be associated with the occurrence of the event

Classification of Causality

The relationship of each AE to the study drug will be recorded on the eCRF in response to the following question:

Is there a reasonable possibility that the study drug caused the AE?

Yes (related) A causal relationship between the study drug and the AE is a reasonable possibility.

No (not related) A causal relationship between the study drug and the AE is not a reasonable possibility.

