9.1.2.2 Follow-Up Period

All subjects, regardless of whether they complete all 24 months of treatment or discontinue study drug prematurely, will complete 2 post-treatment Follow-Up Visits; one 4 weeks after the last dose of study drug and a second 12 weeks after the last dose of study drug (Visit 14 and Visit 15 respectively). If clinically indicated, more frequent safety assessments can be made as unscheduled (UNS) assessments or visits during the post-treatment follow-up period.

In some cases, UNS visits will be needed to follow-up on safety or other findings, and the related assessments (outlined in the Schedule of Assessments) will depend on the reason for the UNS visit, and will be decided at the discretion of the investigator.

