9.3.3 Removal of Subjects from Therapy or Assessment

The investigator may withdraw the subject from the study at any time for safety or administrative reasons. The subject may stop study drug or withdraw from the study at any time for any reason.

Absolute lymphocyte count from the hematology and differential panel will be monitored during the study. Should a subject develop a Grade 2 or greater lymphocytopenia (less than $800/\text{mm}^3$), this should be confirmed as soon as possible but no later than within 5 days with a repeat test of absolute lymphocyte count. If confirmed, study drug administration should be interrupted for a minimum period of 2 weeks and for a maximum period of 4 weeks. Restart of study drug may take place only when absolute lymphocyte count returns to greater than LLN. Absolute lymphocyte count will be measured 4 weeks after restart of study drug. Subsequent measurements of absolute lymphocyte counts will follow the schedule of assessments (Table 3) and any results showing a Grade 2 or greater lymphocytopenia (less than $800/\text{mm}^3$) should be handled as above. If a 2nd occurrence of Grade 2 or greater lymphocytopenia (less than $800/\text{mm}^3$), that is confirmed on repeat testing, occurs within 6 months, then the subject should be discontinued permanently from the study drug. (revised per Amendment 01)

Subjects who discontinue study drug early must complete the ED Visit (within 7 days of the last dose of study drug) and the Follow-Up Visits (1 and 3 months after the last dose of study drug). These Follow-Up Visits will be conducted to monitor efficacy and safety parameters after early withdrawal from the study or discontinuation of study drug.

All subjects who discontinue study drug before reaching 12 months of treatment will also be asked to return to the clinic for a 12-month clinical assessment and then again at 24 months. Subjects who discontinue treatment between 12 and 24 months of treatment will be asked to return to the clinic for a 24 month clinical assessment. Subjects who discontinue early from study drug are considered “on study” as long as they continue to return for their regularly scheduled clinical assessments at 12 and 24 months as outlined above, at which efficacy and quality of life will be assessed along with concomitant medications and AEs. However, subjects who discontinue study drug early are not considered to have ‘completed’ the study as a final Subject Disposition.

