9.5.4.1 Reporting of Serious Adverse Events

All SAEs, regardless of their relationship to study treatment, must be reported on a completed SAE form by email or fax as soon as possible but no later than 24 hours from when the investigator becomes aware of the event.

SAEs, regardless of causality assessment, must be collected up to 12 weeks after the last dose of study drug. All SAEs must be followed to resolution or, if resolution is unlikely, to stabilization. Any SAE judged by the investigator to be related to the study treatment or any protocol-required procedure should be reported to the sponsor regardless of the length of time that has passed since study completion.

The detailed contact information for reporting of SAEs is provided in the Investigator Study File.

For urgent safety issues, please ensure all appropriate medical care is administered to the subject and contact the appropriate study team member listed in the Investigator Study File.

It is very important that the SAE report form be filled out as completely as possible at the time of the initial report. This includes the investigator's assessment of causality.

Any follow-up information received on SAEs should be forwarded within 1 business day of its receipt. If the follow-up information changes the investigator's assessment of causality, this should also be noted on the follow-up SAE form.

Preliminary SAE reports should be followed as soon as possible by detailed descriptions including copies of hospital case reports, autopsy reports, and other documents requested by the sponsor.

The investigator must notify his/her IRB/IEC of the occurrence of the SAE in writing, if required by their institution. A copy of this communication must be forwarded to the sponsor, or its designee, to be filed in the sponsor's Trial Master File.

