9.7.1.8.2 ADVERSE EVENTS

The AE verbatim descriptions (investigator terms from the eCRF) will be classified into standardized medical terminology using the Medical Dictionary for Regulatory Activities (MedDRA). AEs will be coded to the MedDRA (Version 19.0 or higher) lower level term closest to the verbatim term. The linked MedDRA PT and primary system organ class (SOC) are also captured in the database.

A TEAE is defined as:

- An AE that emerges during treatment within 4 weeks of the last dose of study drug, having been absent at pretreatment (Baseline) or
- Reemerges during treatment, having been present at pretreatment (Baseline) but stopped before treatment, or
- Worsens in severity during treatment relative to the pretreatment state, when the AE is continuous.

Only those AEs that are treatment-emergent will be included in summary tables. All AEs, treatment-emergent or otherwise, will be presented in subject data listings.

The TEAEs will be summarized by treatment group on the Safety Analysis Set. The incidence of TEAEs will be reported as the number (percentage) of subjects with TEAEs by SOC and PT. A subject will be counted only once within an SOC and PT, even if the subject experienced more than 1 TEAE within a specific SOC and PT. The number (percentage) of subjects with TEAEs will also be summarized by maximum severity (mild, moderate, or severe). The number (percentage) of subjects with TEAEs will also be summarized by relationship to study drug (Yes [related] and No [not related]).

The number (percentage) of subjects with treatment-related TEAEs will be summarized by SOC and PT. Treatment-related TEAEs include those events considered by the investigator to be related to study drug. The number (percentage) of subjects with treatment-related TEAEs will also be summarized by maximum severity (mild, moderate, or severe).

AEs will be summarized by the following subgroups: region, , prior treatment with AChEIs or memantine (no or yes), and clinical subpopulation (MCI due to AD or the early stages of AD). (revised per Amendment 01)

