The number (percentage) of subjects with TEAEs leading to death will be summarized by MedDRA SOC and PT for each treatment group. A subject data listing of all AEs leading to death will be provided. The number (percentage) of subjects with treatment-emergent SAEs will be summarized by MedDRA SOC and PT for each treatment group. A subject data listing of all SAEs will be provided. The number (percentage) of subjects with TEAEs leading to discontinuation from study drug will be summarized by MedDRA SOC and PT for each treatment group. A subject data listing of all AEs leading to discontinuation from study drug will be provided.

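### In the Amendment 01 text, SAEs and fatal AEs with onset in weeks 5 to 12 after the last dose are collected and listed but not counted by arm

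*Protocol*

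**What the plan says.** **Collection (Amendment 01 text).** Section 9.5.1.5.1 gathers AEs of every kind from consent to Visit 15 and adds that "SAEs will be collected for 12 weeks after the last dose". Section 9.5.4.1 repeats the window whatever the attribution: "SAEs, regardless of causality assessment, must be collected up to 12 weeks after the last dose of study drug". Section 9.1.2.2 schedules two post-treatment visits for everyone, "one 4 weeks after the last dose of study drug and a second 12 weeks after the last dose of study drug" (Visits 14 and 15). Section 9.3.3 gives their purpose for subjects who stop early: "These Follow-Up Visits will be conducted to monitor efficacy and safety parameters after early withdrawal from the study or discontinuation of study drug".

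**Analysis (same text).** Section 9.7.1.8.2 uses a shorter window. The first limb of its TEAE definition is "An AE that emerges during treatment within 4 weeks of the last dose of study drug". The other two limbs (re-emergence and worsening) refer to treatment only. The section then states: "Only those AEs that are treatment-emergent will be included in summary tables". For deaths, "The number (percentage) of subjects with TEAEs leading to death will be summarized by MedDRA SOC and PT", by treatment group. The SAE table is restricted in the same way, to treatment-emergent SAEs. Everything else goes to subject listings: one of all AEs, one of all SAEs and one of all AEs leading to death. The original protocol has the same rules.

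**Later version.** The Version 7.0 synopsis limits collection of new AEs to 4 weeks after the last dose, with follow-up to 12 weeks. It says nothing separate about the SAE window.

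**The concern.** The protocol treats weeks 5 to 12 as a period in which safety still has to be watched. It brings every subject back at week 12 and requires SAEs to be reported throughout. For a Grade 2 or worse lymphocytopenia found at Visit 14 or 15, Section 9.5.1.5.1 also asks for repeat counts until it resolves or a cause other than the drug is confirmed. Yet a serious infection that began in week 10 would enter no table by arm.

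This is not a detail left to the SAP. The protocol fixes the exclusion with the word 'only', and the death and SAE tables are worded to match. As written, the report could not state all deaths and all SAEs by randomised arm over the SAE collection window that the protocol itself sets.

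**Working it through.** **Inputs**
- End of SAE collection: last dose + 12 weeks = 84 days (Sections 9.5.1.5.1 and 9.5.4.1).
- End of the treatment-emergent window: last dose + 4 weeks = 28 days (Section 9.7.1.8.2, reading the first limb as during treatment or up to 4 weeks afterwards).
- Treatment: 104 weeks. Visit 13 is Day 729, Visit 14 Day 757 and Visit 15 Day 813 (Table 3).
- Randomised: 1330, or 665 per arm, with 30% dropout assumed (Section 9.7.2).

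**Reproducing the protocol's schedule.** 729 + 28 = 757 and 729 + 84 = 813. Both match Table 3, so the two windows end at Visits 14 and 15.

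**Size of the gap**
- Days collected but not tabulated: 84 − 28 = 56.
- Share of the post-treatment collection period: 56/84 = 67%.
- Share of a completer's time from first dose to Visit 15: 8/(104 + 12) = 8/116 = 6.9%.
- Follow-up affected if all 1330 reach Visit 15: 1330 × 56/365.25 = 203.9 subject-years, or 665 × 56/365.25 = 102.0 per arm.
- If the 30% assumed to drop out contributed nothing to these weeks: 0.70 × 203.9 = 142.7 subject-years.

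**What falls into the gap.** The rule turns on when the AE began, not on when the subject died.

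| AE onset | Outcome | Counted by arm? |
|---|---|---|
| On treatment or by week 4 | SAE, or death at any later date in follow-up | Yes |
| Weeks 5 to 12 after last dose | SAE or death | No, listed only |

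**Number of events.** The protocol gives no SAE rate. Purely as an assumption, 2 to 15 SAEs per 100 subject-years would give 102.0 × 0.02 = 2.0 to 102.0 × 0.15 = 15.3 SAEs per arm in the gap.

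**The case against.** The strongest reply is that a time-limited treatment-emergent table with full listings is a common reporting choice, and that collecting for longer than one tabulates is not a contradiction. The events are not lost: all SAEs and all fatal AEs are listed, the DSMB reviews cumulative safety data, and disposition by arm shows AE as a reason for withdrawal. Much of this stands. No efficacy result, alpha or power is affected, and no data collection is at fault. But a listing gives no count or percentage by arm, and neither the DSMB review nor the disposition table is a planned tabulation of late deaths or SAEs.

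A second reply concerns version. The quoted sections belong to Amendment 01. The revision history records later changes to AE handling after discontinuation (Amendment 05) and to the TEAE definition (Amendment 03). The logged TEAE change concerns its start, and no change to the SAE window or to the restricting sentence is logged. Silence in a log and a synopsis still does not show what Version 7.0 says, so this objection stands as a limit on the point.

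Several stronger readings are tempting and not supported:
- *No death in weeks 5 to 12 is compared.* Deaths from AEs that began by week 4 remain in the table.
- *Subjects stopped for rash, infection or lymphocytopenia are the likeliest to have late serious events.* The protocol does not say so. Their index event is already treatment-emergent if it began on drug. In the multiple-dose study (Section 7.1), lymphocyte effects gradually resolved between 6 and 21 days after the last dose, inside the 4-week window, although that study dosed for only 14 days.
- *The loss is 291 subject-years.* That is 1900 × 8/52.18, but 1900 pools studies 301 and 302. At the minimum of 850 for this study alone the figure is 850 × 56/365.25 = about 130.

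**Conclusion.** The point holds for the Amendment 01 text, within the limits above. It is a stated exclusion rule with a modest effect: two thirds of the post-treatment SAE window, but only about 7% of a completer's follow-up. The 204 subject-years is an upper bound that assumes every subject reaches Visit 15. How many events are involved is unknown, and so is whether the gap survives in Version 7.0. It is worth correcting because deaths and SAEs by arm are basic to a trial meant to support registration and the data are already being gathered. It is an inexpensive improvement to reporting, not a flaw that threatens the trial's conclusions.

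**What to change.** In Section 9.7.1.8.2:
1. Keep the treatment-emergent tables as they are.
2. Add two summaries by randomised arm on the Safety Analysis Set: all deaths, and all SAEs by SOC and PT. Each should run from first dose through 12 weeks after the last dose, regardless of treatment-emergent status.
3. Show separately, by arm, any deaths or SAEs recorded later at the 12- or 24-month returns of early discontinuers. Section 9.3.3 and Table 3 have AEs assessed at those returns, which can fall well after Visit 15, so the main summaries need a stated cut-off.
4. Reword the restricting sentence: 'Except for the summaries of all deaths and all SAEs, only treatment-emergent AEs will be included in summary tables.'

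Before making the change, check the Version 7.0 sections on AE collection and analysis to see whether the two windows still differ.

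The cost is two tables, a small supplementary display and one sentence, all from data already collected. No visit, treatment, sample size or alpha changes. The downside is that some off-drug events unrelated to treatment will be added to both arms.
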